### **1.3 Rationale for starting dose and dosing schedule**

Ruxolitinib will be administered orally to patients, as per standard of care (SOC), at a dose of 10 mg BID as indicated in the product monograph for patients with cGvHD. Patients may require dose reductions or modifications of ruxolitinib during the course of treatment based on side effect profile, clinical assessment, and laboratory assessments. No dose increases above 10 mg BID will be allowed in the study due to the very limited clinical experience with such doses in patients with GvHD. After an initial 4 weeks of therapy with ruxolitinib monotherapy, patients will also receive the investigational medicinal product

(IMP) belumosudil orally at a dose of 200 mg OD or 200 mg BID (if on a proton pump inhibitor (PPI)) as based on the published activity and safety data in the ROCKstar trial. Several real-world experience studies reported no significant toxicity profile or drug-drug interaction issue from combination of ruxolitinib and belumosudil. Dose reductions and modifications are described in Section 5.3. Patients will remain on dual therapy for an additional 48 weeks until progression of cGVHD, or intolerance to either agent, whichever occurs sooner.

## **2. STUDY DESIGN**

This is a phase II non-randomized, open-label study in patients with moderate to severe cGvHD who have failed to respond to, or are intolerant of first line therapy. Patients will receive combination therapy with two oral agents (belumosudil, ruxolitinib) with documented individual efficacy as second line in cGVHD treatment. A maximum of 63 participants are expected to be enrolled in Canada.

[figure not shown]
Participants will begin on 10 mg BID of oral ruxolitinib alone for one cycle (i.e. Cycle 1). Each cycle is equal to 28 days. Starting at cycle 2, they will take belumosudil in addition to ruxolitinib, at a dose of 200 mg OD or 200 mg BID (if on a PPI). Patients will remain on dual therapy for 48 weeks (i.e. 12 cycles), until progression of cGVHD, or intolerance to either agent, whichever occurs sooner. A safety visit will be conducted at the end of treatment, 28 days following end of treatment, as well as a remote follow up visit conducted 24 weeks following end of treatment.

The end points will include overall response rates at 24 weeks on treatment and failure-free survival at 48 weeks on treatment (i.e., 28 and 52 weeks on combination therapy) which adopts composite endpoints including: (1) requirement of additional treatment or switch over, (2) progression or flare-up of GvHD with/without ruxolitinib tapering, and (3) death from relapse/non-relapse mortality.

### **2.1 Estimated Study Duration**

The enrollment period of the study is expected to be approximately 12-18 months. The screening period may last up to 14 days. The treatment period for an individual patient is expected to be approximately 52 weeks from the date of starting therapy (i.e., Cycle 1 Day 1). Patients will be followed for evidence of progression of cGVHD, survival, and unexpected toxicity (if any) for 24 weeks after the end of treatment visit.

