Study Design:	This is a phase II, non-randomized, open-label study in patients with moderate to severe cGvHD who have failed to respond or are intolerant of first-line steroid therapy. Patients will receive combination therapy with two oral agents (belumosudil, ruxolitinib) with documented individual efficacy as second line treatment in cGvHD patients.

	Participants will begin on 10 mg BID of oral ruxolitinib monotherapy for one cycle (i.e. Cycle 1). Each cycle is equal to 28 days. Upon the initiation of Cycle 2, patients will begin taking belumosudil in addition to ruxolitinib, at a dose of 200 mg OD or 200 mg BID (if on a PPI). Patients will remain on combination therapy for 48 weeks (i.e. 12 cycles), until progression of cGVHD, or intolerance to either agent, whichever occurs sooner. A visit will be conducted at the end of treatment, 28 days post-end of treatment as well as 24 weeks (6 months) post-end of treatment.
Duration:	The enrollment period of the study is expected to take 12-18 months. The screening period for each patient may last up to 14 days. The treatment period for an individual patient is expected to be approximately 52 weeks from the date of starting therapy (Cycle 1 Day 1). Patients will be followed for evidence of progression of cGVHD, survival, and unexpected toxicity (if any) for 24 weeks after the end of treatment visit.
Planned Total Sample Size:	A maximum of 63 patients will be enrolled.
Investigational Product Administration:	Belumosudil will be administered as an oral dose of 200 mg OD or 200 mg BID (if patient is on a proton pump inhibitor (PPI))

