	
End of Treatment Visit
 
 
• Physical Examination & ECOG
 
• Vital Signs
 
• Hematology
 
• Serum Chemistry
 
• AE Assessment
 
• Concomitant Medications
 
• NIH consensus based GvHD organ specific score and global severity score (i.e. mild vs moderate vs severe grade)
 
• Modified Lee Symptom Scale
 
• P-ROM (Photographic Range-Of-Motion) assessment
 
• Pulmonary Function Test
 
• IP return and accountability
 
• Correlative Samples
 
 
Follow-up Visit
 
 
• Survival status
 
• Concomitant Medications (new cGvHD therapies only)
 

Response:	
- Overall response rate (ORR) will be evaluated at 24 and 48 weeks after initiation of combination therapy
 
- Failure-free survival (FFS) will be evaluated using Kaplan-Meier method. The FFS rate will be evaluated at 24 and 48 weeks after initiation of combination therapy
 
- Durable response after response achievement will be evaluated only in the patients who achieved CR or PR during the treatment period (any response)

Safety Variables & Analysis:	
The safety and tolerability of study treatment will be evaluated by means of AE reports, physical examinations, and laboratory safety evaluations. Terminology Criteria for Adverse Events (CTCAE) V5.0 will be used for grading of AEs.
 
Interim safety data will be examined on an ongoing basis to ensure patient safety.

Statistical Analysis:	
Statistical Analysis: This is a single-arm phase II study with a sample size of 63 patients (accounting for 10% dropout) to provide 90% power to detect an improvement in ORR from 49.7% (null) to 66% (alternative) at 6 months using a two-sided exact test at <math>\alpha=0.10</math>
 
Populations:
 
 
- Intent-to-Treat (ITT): All enrolled patients.
 
- Safety: All patients receiving <math>\geq 1</math> dose of belumosudil.
 
- Efficacy: All patients completing <math>\geq 1</math> cycle of belumosudil with baseline assessment.
 

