## 8. STUDY CALENDAR

	Screening	Treatment									End of Treatment and Follow Up		
Visit Name	Screening	C1D1 Week 0 o	C1D14 Week 2	C2D1 Week 4 i	C2D14 Week 6	C3D1 Week 8	C5D1 Week 16	C8D1 Week 28	C11D1 Week 40	C13D28 Week 52	EOT Visit m	28 Day Safety FU Visit	6 Month FU Visit h
Visit Window	-14 days	Within 3 days of enrolment	+/- 2 days	+/- 4 days	+/- 4 days	+/- 7 days	+/- 7 days	+/- 7 days	+/- 7 days	+/- 7 days	+/- 7 days	+/- 7 days	+/- 28 days
Informed consent***	X												
Inclusion/Exclusion Criteria	X												
Demographics	X												
Prior GvHD Medication & Medical History	X												
Tuberculosis Skin Test / Interferon -gamma release assay f	X												
Ruxolitinib Dispensing k		X	X	X	X	X	X	X	X	X k			
Belumosudil Dispensing l				X i	X	X	X	X	X	X l	Taper & Discontinue		
Physical Examination a & ECOG performance status assessment	X	X	X	X	X	X	X	X	X	X	X	X	
Vital Signs b	X	X	X	X	X	X	X	X	X	X	X	X	
P-ROM assessment	X	X	X	X	X	X	X	X	X	X	X	X	
12 Lead ECG c	X												
Pregnancy Test d	X	X											
Hematology e	X	X	X	X	X	X	X	X	X	X	X	X	
Serum Chemistry f	X	X	X	X	X	X	X	X	X	X	X	X	
Virology j	X												
Pulmonary Function Test		X					X	X	X	X	X		
Modified Lee Symptom Scale		X		X		X	X	X	X	X	X		
NIH consensus based GvHD organ specific		X	X	X			X	X	X	X	X		

score and global severity score q													
IP return and accountability			X	X	X	X	X	X	X	X	X l		
Survival Status												X	X
Adverse Events l		Continuous											
Concomitant medications review	X	Continuous											X n
Correlative Samples (optional sub-study) q	X							X			X		

\*\*\*Consent should be done prior to any study specific screening assessment, according to the site ethics board approved process and site institutional timelines. Site should follow their site guidelines for consenting window (timeframe for prior to screening and prior to enrollment). Patient enrollment with Ozmosis@UHN is required. Please refer to section "Patient Enrollment".

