- In the event that at the intended C2D1 visit assessment the participant is experiencing Grade  $\geq 3$  AE(s), treatment with belumosudil should not begin. This visit will be considered an unscheduled visit and the C2D1 visit should be rescheduled. The participant can continue on ruxolitinib alone and should be followed for resolution of the Grade  $\geq 3$  AE(s). If the Grade  $\geq 3$  AE(s) improve to Grade  $\leq 2$  or resolve completely within 4 weeks, the participant will still be eligible to receive belumosudil. In this case, they should come back in for a true C2D1 visit and can complete all the necessary assessments as well as belumosudil dosing. If the Grade  $\geq 3$  AE(s) does not recover within 4 weeks, the participant will move on to the End of Treatment visit and discontinue study. If there are any questions or concerns about the patient status and treatment in these scenarios, this should be discussed with the sponsor.
- HIV, HBsAg, HBV DNA, HCV antibody, and HCV RNA.
- Ruxolitinib may continue on past the C13D28 visit as per standard of care and if, in the opinion of the treating investigator, the patient is receiving clinical benefit. Tapering of ruxolitinib should be done slowly as per the product monograph with documented CR or PR, starting with a 50% dose reduction every 2 months (56 days). Initial dose reduction is to 5 mg orally BID. If sustained cGvHD response is observed (i.e. no worsening of cGvHD signs and symptoms), patient is further tapered by a second 50% dosage reduction to 5 mg orally QD for an additional 2 months (56 days), prior to cessation.
- Patients whose cGVHD has not progressed at the time of study treatment completion or discontinuation of combination treatment of belumosudil and ruxolitinib for reasons other than AEs should be tapered off belumosudil by reducing the dose every 2 weeks (14 days) as described below:  
Starting dose of 200mg BID  $\rightarrow$  200mg QD  $\rightarrow$  200mg QOD  $\rightarrow$  Discontinue **OR** Starting dose of 200mg QD  $\rightarrow$  200mg QOD  $\rightarrow$  Discontinue
- For those participants who completed all treatment visits, the C13D28 visit can be considered the End of Treatment Visit.
- Only subsequent therapies used to treat cGvHD need to be captured during the period from the 28-day safety follow up and the 6 month follow up visit

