### **10.5 Adverse Events of Special Interest**

An adverse event of special interest (AESI) is an AE (serious or non-serious) of scientific and medical concern specific to the Sponsor’s product or program, for which ongoing monitoring and rapid communication by the Investigator to the Sponsor is required. Such events may require further investigation in order to characterize and understand them. AESIs may be added, modified, or removed during a study by protocol amendment.

AESIs for this study include:

- Grade  $\geq 3$  infections: Severe infections (e.g., bacterial, viral, or fungal) that are life-threatening or require significant medical intervention.
- Secondary malignancies: New cancers that develop during the study, potentially linked to the treatment.
- Grade  $\geq 3$  blood pressure changes: Severe hypertension or hypotension that could pose significant health risks.
- Grade  $\geq 3$  ALT, AST, and bilirubin: Severe liver function abnormalities, indicated by elevated levels of alanine aminotransferase (ALT), aspartate aminotransferase (AST), or bilirubin, suggesting potential liver toxicity.

- Symptomatic overdoses: Any symptoms resulting from taking higher-than-prescribed doses of ruxolitinib or belumosudil, requiring immediate attention.

These AESIs are monitored closely to ensure participant safety and to gather data on the safety profile of the combination therapy for cGvHD.

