### **10.7 Adverse Event Reporting Period and Follow up of AEs, SAEs, and AESIs**

The AE reporting period begins at the time the patient receives their first dose of study treatment (i.e., C1D1). All AEs, SAEs and AESIs must be followed until resolution or 28 days following the last dose of study treatment, whichever comes first. The QI shall provide follow-up information when available in a new follow-up SAE form. Resolution status of such an event should be documented on the eCRF.

Patients withdrawn from the study due to an AE will be followed until the AE has resolved. In the case of an SAE, the patient will be followed until clinical recovery or until progression has been stabilized or judged to be chronic. After discontinuation from protocol treatment, all patients will be followed for any ongoing or late toxicities. Patients will be seen for a Safety Follow up visit,  $28 \pm 7$  days after discontinuing treatment. Safety Follow up procedures will be completed as indicated in the Study Calendar.

The AE reporting period will end once 28 days have passed since the patient's last dose of study drug. Therefore, SAEs occurring after the last dose of study treatment that have been deemed by the QI as at least possibly related to protocol treatment, must be reported if it occurs within 28 days after discontinuation of the investigational products. In addition, any known untoward event of any severity that occurs subsequent to the AE reporting period that the Investigator assesses as at least possibly related to the study therapy (i.e., the relationship cannot be ruled out) should also be reported as an AE. Ongoing and non-resolved toxicities are followed until resolution back to baseline or  $\leq$  Grade 1 after off treatment, or until considered stable by the QI.

---

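### The protocol states 24 weeks of post-treatment toxicity follow-up, but the 6-month contact lists no toxicity enquiry and AE reporting closes 28 days after the last dose

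*Protocol*

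**What the plan says.** **What is stated.** Section 2.1 commits to follow-up for progression, "survival, and unexpected toxicity (if any) for 24 weeks after the end of treatment visit". The Duration row of the synopsis likewise names "unexpected toxicity (if any) for 24 weeks after the end of treatment visit". Section 10.7 adds that, once off protocol treatment, every patient is followed for toxicity that is ongoing or late.

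**What is scheduled.** Section 2 describes the last contact as "a remote follow up visit conducted 24 weeks following end of treatment". The synopsis gives it two items: survival status and "Concomitant Medications (new cGvHD therapies only"). The End of Treatment list just above it does include an AE assessment. In the Section 8 calendar, the separate marks in the 6-month column are for "Survival Status" and concomitant medications. A footnote to the medication row says "Only subsequent therapies used to treat cGvHD need to be captured during the period from the 28-day safety follow up" to the 6-month visit. The AE row reads *Continuous* from C1D1.

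**When reporting stops.** Section 10.7 says "The AE reporting period will end once 28 days have passed" since the last dose of study drug. Beyond that point it still asks for any known event, of any severity, that the investigator considers at least possibly related.

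**What is of special interest.** Section 10.5 lists "Secondary malignancies: New cancers that develop during the study, potentially linked to the treatment".

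**The concern.** The statement of purpose and the data collection do not match. Toxicity over 24 weeks is a named object of follow-up, yet nothing listed for the one contact in the later part of that period asks about it. Whether a late event reaches the database depends on the investigator already knowing of it and judging it at least possibly related. A new cancer that the patient does not mention, or that is judged unrelated, has no stated collection route after the reporting period closes. Section 10.5 nevertheless defines the AESI over the whole study, which includes this follow-up.

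What is at stake is how a late-safety count can be read. A count built on passive reporting has no clear denominator of patients who were asked, so a low or zero count cannot be separated from incomplete enquiry. Section 1.2 says that no prospective study has examined two non-first-line agents together in cGvHD, and safety is a primary objective. Late safety data therefore have value here.

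**Working it through.** The protocol gives no figure for this gap, so there is nothing to reproduce. The check compares the provisions and then applies simple arithmetic to the protocol's own time windows.

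**Step 1: statement against collection**

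| Source | Content after end of treatment (EOT) |
|---|---|
| Synopsis (Duration), Section 2.1 | Progression, survival and unexpected toxicity for 24 weeks |
| Synopsis (Follow-up Visit) | Survival status; new cGvHD therapies |
| Section 8 calendar, 6-month column | Separate marks for survival status and concomitant medications; AE row *Continuous*, end not visible |
| Section 10.7 | AE period ends 28 days after last dose; the only visit named is the 28 ± 7 day safety visit; later events reportable if known and at least possibly related |

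No listed item at the 6-month contact carries out the 24-week toxicity statement.

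**Step 2: length of the uncovered period**

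Let L be the number of weeks from EOT to the last dose of study drug. The AE period closes 28 days (4 weeks) after the last dose, so

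uncovered weeks = 24 − (L + 4).

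- **All dosing stops at EOT.** L = 0, so 24 − 4 = 20 weeks, and 20/24 = 83%.
- **The belumosudil taper sets the last dose.** Section 5.4 starts the taper at EOT and says it lasts 4 weeks. L = 4, so 24 − 8 = 16 weeks, and 16/24 = 67%.
- **Continued ruxolitinib counts as study drug.** As an illustration, take the two 56-day taper steps of Section 5.4 starting at EOT. L = 112/7 = 16, so 24 − 20 = 4 weeks, and 4/24 = 17%. With L of 20 weeks or more, nothing is left uncovered by the reporting period.

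These are nominal times. The visit windows (± 7 days at EOT, ± 28 days at 6 months) are ignored.

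**Step 3: which case applies**

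The protocol does not settle this. Section 10.7 opens the AE period at C1D1, when only ruxolitinib is given, and Section 10.3 requires attribution to each study drug. Both suggest that ruxolitinib counts. On the other hand, Sections 1.3 and 5.1 name belumosudil as the investigational product and treat ruxolitinib as standard of care. The Section 8 footnotes allow ruxolitinib to continue beyond C13D28 on that basis. In every case, the synopsis list for the 6-month contact has no toxicity item.

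**The case against.** The strongest reply is that late toxicity is not abandoned:

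- Section 10.7 makes reporting of known, possibly related late events mandatory.
- The same section has unresolved toxicities followed to baseline, Grade 1 or less, or stability.
- Section 10.4 requires later deaths judged possibly related to be reported promptly.
- The calendar's AE row reads *Continuous* and may extend into the 6-month column.
- The 24-week statement covers only unexpected toxicity, if any, which could be read as met by this duty.

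Much of this stands. A reader might infer that late events are not reportable, or that the calendar excludes AE collection at 6 months. The documents support neither. The accurate statement is that active enquiry is not listed. The AE row does not remove the point, however. The medication row is also marked *Continuous*, yet it carries its own mark at 6 months. If the AE row did run that far, it would conflict with the synopsis list and with the 28-day closure in Section 10.7. The duty to report a known event also does not make it known at a remote contact where nobody is listed to ask.

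It is also fair to say that no analysis of events after the 28-day window is specified, and that trimming one phrase would remove the inconsistency. That would make the text consistent but would leave late AESIs without active enquiry.

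**Conclusion.** The mismatch holds and is worth correcting, as an inexpensive improvement to late-safety and AESI ascertainment. The period without AE reporting other than of known, possibly related events is about 20 of 24 weeks if all dosing stops at EOT. It is about 16 if the 4-week belumosudil taper sets the last dose, and shorter if continued ruxolitinib counts. No single figure is right for all patients while that definition stays open.

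Two stronger readings should be resisted. First, a reader might infer that the primary safety result is compromised. It is not: Sections 3 and 11.3.1 define that endpoint over the treatment duration. Second, a reader might want a number of late events that would be missed. The documents give no late-event rate and no basis for the share that passive reporting would fail to capture, so none can be stated.

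The conclusion rests on the synopsis follow-up list and on Section 10.7. It does not depend on where the calendar's AE row ends.

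**What to change.** 1. In the 6-month column of the calendar and in the synopsis follow-up list, add one question with one eCRF line. It should cover related SAEs and all AESIs since the 28-day visit, including new malignancy regardless of attribution.
2. Summarise these events separately from AEs within the 28-day window, with the number of patients asked as the denominator.
3. Align Section 10.7 and the calendar AE row with this, and show where the AE row ends. State whether ruxolitinib continued after end of treatment counts as study drug when the last dose is determined.
4. At minimum, if nothing is added, narrow the 24-week statement in the synopsis and Section 2.1 to what is collected. The same sentence promises follow-up for cGvHD progression, for which the contact lists only new cGvHD therapies, so check that wording too.

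The cost is one more question at a remote contact already scheduled, and a small amount of data entry. No extra visit is needed.

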## 2.2 Study Schema

\*Patients are permitted to receive a steroid dose at the time of enrollment, given it is <0.5mg/kg/day of prednisone or equivalent

\*Ruxolitinib may continue on past the C13D28 visit as per standard of care if, in the opinion of the treating investigator, the patient is receiving clinical benefit. Tapering of ruxolitinib should be done slowly as per the product monograph with documented CR or PR, starting with a 50% dose reduction every 2 months (56 days). Initial dose reduction is to 5 mg orally BID. If sustained cGvHD response is observed (i.e. no worsening of cGvHD signs and symptoms), patient is further tapered by a second 50% dosage reduction to 5 mg orally QD for an additional 2 months (56 days), prior to cessation.

**Figure 1. Participant treatment schema**

## 3. OBJECTIVES

Primary Objectives	Primary Endpoints
To evaluate efficacy, tolerability and safety of combination treatment of belumosudil with ruxolitinib as second line therapy for steroid-refractory cGvHD.	
 
Efficacy will be assessed using overall response rate (ORR) as per the NIH cGvHD Consensus Response Criteria at 24 weeks of combination treatment (C8D1) of belumosudil with ruxolitinib (i.e., 28 weeks after C1D1).
 
Tolerability and safety will be assessed by the incidence and severity of adverse events (AEs) throughout the treatment duration using CTCAE v5.0 grading.
 

Secondary Objectives	Secondary Endpoints
To evaluate the response achievement with combination treatment of belumosudil with ruxolitinib as second line treatment for cGvHD.	
 
ORR as per the NIH cGvHD Consensus Response Criteria after 48 weeks of combination treatment of belumosudil with ruxolitinib (i.e., 52 weeks after C1D1).
 
Failure-free survival (FFS) after 24 and 48 weeks of combination treatment of belumosudil with ruxolitinib (i.e., 28 and 52 weeks after C1D1). FFS is defined as the time from treatment initiation until the occurrence of treatment failure.
 
Durable response rate in patients who achieve complete or partial response with combination treatment of belumosudil with ruxolitinib as assessed at 52 weeks from
 

	
C1D1. Durable response is defined as sustained improvement in symptoms or absence of disease progression from the time of treatment initiation.
 
4. Overall GvHD symptom burden improvement, serially measured with a modified Lee Symptom Scale (see Appendix D).

Exploratory Objectives	Exploratory Endpoints
To evaluate improvement in musculoskeletal involvement of sclerotic GvHD using the P-ROM score measurement.	1. Changes in the P-ROM score after 12, 24, and 48 weeks of combination therapy in patients who have developed sclerotic GvHD in musculoskeletal involvement of GvHD

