### **7.3 Response Duration**

Response duration will be defined as the time from the first documented achievement of complete response (CR) or partial response (PR), whichever occurs first (as defined in Table 7), until the first documented date of loss of response or disease progression. The smallest measurements recorded during the study, including baseline, will serve as the reference for assessing progression.

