## 11.3 Evaluation of Study Endpoints

### 11.3.1 Evaluation of the Primary and Secondary Endpoints

Overall response rate (ORR) will be evaluated at 24 and 48 weeks after combination therapy (i.e. 28 and 52 weeks after enrollment), respectively. The proportion of responders and its 95% confidence interval (using exact binomial methods) will be calculated.

Failure-free survival (FFS) will be evaluated using Kaplan-Meier method. The FFS rate will be evaluated at 24 and 48 weeks after combination therapy (i.e. 28 and 52 weeks after enrollment), The composite endpoint of failure is defined as 1) GvHD progression or loss of response requiring switch of systemic GvHD treatment, 2) relapse of primary hematologic disease and 3) non-relapse mortality.

Durable response after response achievement will be evaluated only in the patients achieved CR or PR (any response). The Kaplan-Meier estimate will be calculated from the date of CR/PR achievement to the date of losing response/progression or death from any cause.

GvHD symptom burden improvement, measured serially by the modified Lee Symptom Scale, will be evaluated using repeated measure based on the general linear model. If p-value is less than 0.05, it demonstrates statistically significant change over time within subject.

The Modified Lee symptom score (mLSS) will be used to reflect a symptom burden in cGvHD study patients. The symptoms will be assessed serially and will be evaluated using repeated measure based on the general linear model. If p-value is less than 0.05, it demonstrates statistically significant change over time within subject. The score assesses 7 different organs/areas including skin, eye/mouth, breathing, eating/digestion, muscle/joints, energy, and mental/emotional health. The sum of these domains will be calculated to derive the total mLSS. Clinically meaningful improvement in mLSS is defined as a reduction of  $\geq 7$  points in overall mLSS. Longitudinal change in mLSS is analyzed by repeated measures using generalized linear model over time, evaluating within-subject and between-subject effects. In addition, the proportion of the patients showing clinically meaningful improvement in mLSS is analyzed longitudinally at 12, 24, and 48 weeks. In addition, the best improvement in mLSS is also calculated in each subject and plotted.

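### Secondary endpoint 3 (durable response) has incompatible definitions, and the Section 3 wording, read literally, can count some lost responses as durable

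*Protocol*

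**What the plan says.** Section 3 (secondary endpoint 3), repeated in the synopsis, names the measure as "Durable response rate in patients who achieve complete or partial response with combination treatment of belumosudil with ruxolitinib as assessed at 52 weeks from" C1D1, and continues: "Durable response is defined as sustained improvement in symptoms or absence of disease progression from the time of treatment initiation".

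The synopsis, under Response, takes as the population "only in the patients who achieved CR or PR during the treatment period (any response".

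Section 7.3 states: "Response duration will be defined as the time from the first documented achievement of complete response (CR) or partial response (PR), whichever occurs first". The interval runs "until the first documented date of loss of response or disease progression". The same section makes the smallest measurement recorded on study the reference for progression.

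Section 11.3.1 states: "The Kaplan-Meier estimate will be calculated from the date of CR/PR achievement to the date of losing response/progression or death from any cause". The synopsis, under Analyses, also lists durable response as a Kaplan-Meier estimate.

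Three other places bear on the reading:
- Section 7.2 has each organ compared with its C1D1 status.
- Table 7 exempts a rise from 0 to 1 from progression for skin, eyes, esophagus, upper and lower GI, and the lung symptom score.
- Section 5.6 treats a lack of response or a mixed response as a progression event for analysis.

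**The concern.** The *or* in Section 3 makes absence of progression sufficient on its own for any patient who has had a CR or PR. Loss of response is not mentioned, no minimum duration is set, and the clock starts at treatment initiation rather than at the response. The alternative branch, symptom improvement, refers to no NIH criterion and no threshold.

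Sections 7.3 and 11.3.1 name loss of response separately from progression, so leaving it out of Section 3 changes who counts as durable. Sections 1.2 and 12 give the rarity of complete and lasting responses as a reason for the combination, so this endpoint carries part of the trial's argument. In an open-label single-arm trial, an unresolved definition can also end up being chosen after the data are known.

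**Working it through.** No figure in the protocol depends on this endpoint, so there is none to reproduce. The check is a comparison of texts, then a count of logical cases.

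**1. Side by side**

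| Place | Measure | Clock starts | Fails or ends at |
|---|---|---|---|
| Section 3, synopsis | rate at week 52 | treatment initiation | progression (or no sustained symptom improvement) |
| Section 7.3 | duration | first CR/PR | loss of response, progression |
| Section 11.3.1 | Kaplan-Meier | CR/PR | loss of response, progression, death |

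The type of measure, the time origin and the end event all differ between Section 3 and Section 11.3.1.

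**2. Can a lost response be durable under Section 3?** Take one organ scored 0 to 3, baseline 1, 2 or 3, with the scheduled NIH assessments at weeks 16, 28, 40 and 52. Following Table 7, response means a score of 0 or at least 1 point below baseline. Progression means a rise of at least 1 point from the reference, except 0 to 1. Loss of response, which the protocol does not define, is taken as no longer meeting CR or PR.

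- All paths: 3 × 4^4 = 768.
- Paths with a response at some visit: (256 − 3^4) + (256 − 2^4) + (256 − 1^4) = 175 + 240 + 255 = 670.

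| Reference for progression | No progression (durable, Section 3) | of these, response lost at some point | of these, out of response at week 52 |
|---|---|---|---|
| C1D1 baseline (7.2) | 350 | 196 | 96 |
| Nadir (7.3) | 101 | 11 | 7 |

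The 11 nadir cases all start from score 1 and come from the 0-to-1 exemption. There are 2^4 − 1 = 15 paths that use only scores 0 and 1 and include a 0; 4 of them never lose the response, and 15 − 4 = 11. An example is baseline 1, then 0, 1, 1, 1: a CR lost at the second assessment, with no progression under either reference. By contrast, baseline 2, then 1, 2, 2, 2 is free of progression against baseline but progresses against the nadir. These are logical cases for one organ, not expected frequencies.

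**3. Liver.** Table 7 sets PR at a 50% decrease and progression at an increase of 2 × ULN. ALT going 3 → 1.5 → 3 × ULN reaches PR (1.5/3 = 50%) and loses it. The rise from nadir is 3 − 1.5 = 1.5 × ULN, short of progression. A baseline of 3 × ULN is within the eligibility limit of 5 × ULN.

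**4. First response at week 52.** Baseline 2, then 2, 2, 2, 1 has no Table 7 progression and a PR at week 52. Section 3 counts it as durable, with zero observed duration. Six such paths exist under either reference. The study calendar schedules no NIH scoring after the end-of-treatment visit. If Section 5.6 is applied at every visit, this patient already has an event at week 16 and is not durable.

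**5. Entry event.** Section 3 requires a response with combination treatment; the synopsis accepts any response in the treatment period. The calendar scores NIH organs at C1D14, before belumosudil, and at C2D1, the day it starts. Responses to ruxolitinib alone can therefore enter under the synopsis wording.

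**6. Leverage per patient.** The number of responders is unknown. Assuming between 37 (the success threshold in Section 11.1) and 63 (all enrolled) ever-responders, each reclassified patient moves a week-52 rate by 100/37 = 2.7 down to 100/63 = 1.6 percentage points. How many would be reclassified is not derivable.

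**The case against.** The strongest reply has four parts.

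- **Nadir.** A reader might infer that every PR drifting back to its baseline score is counted as durable. Section 7.3 judges progression against the smallest recorded measurement, and on that reference most such drifts are progression. This stands: the lost-response paths fall from 196 to 11. It does not close the gap, because the 0-to-1 and liver cases remain and Section 7.2 still points to C1D1.
- **Section 5.6.** If lack of response is a progression event at each visit, the week-52 first responder drops out and, on a broad reading, so do lost responses. This is possible but not stated. The sentence sits in text about patients who continue treatment, and Section 3 does not refer to it. Applied from treatment initiation, it would also disqualify anyone not yet responding at week 2 or 4, although Section 1.2 says belumosudil's effect can take 3 to 6 months. The symptom branch would stay open in any case.
- **The analysis is Kaplan-Meier.** A reader might infer that the reported durability is bound to be inflated. Section 11.3.1 already counts lost responses as events, and a week-52 first responder contributes essentially no follow-up there. This stands: the inflation occurs only if the Section 3 rate is what gets reported. The protocol asks for both.
- **Scope.** Section 7.3 defines response duration rather than durable response, so its silence on death is a minor point. Section 2.1 does promise follow-up for progression for 24 weeks after end of treatment, but the calendar schedules no NIH scoring in that period.

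**Conclusion.** The definitions conflict, and the Section 3 wording is wrong for an endpoint called durable response. How far it misclassifies depends on two matters the protocol leaves unsettled: the reference for progression (7.2 or 7.3) and the reach of Section 5.6. Against C1D1, any PR that returns to its baseline score stays durable; against the nadir, only cases such as a CR lost by a 0-to-1 rise and some liver paths do. A first response at week 52 counts as durable unless Section 5.6 is applied at every visit.

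The number of patients affected cannot be derived from the protocol, so no overall size or certain upward bias can be claimed. The primary ORR, the sample size and the success rule are untouched. This is a secondary endpoint without a formal test. It should be fixed, but it does not threaten the main conclusion.

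**What to change.** - In the synopsis (endpoint and Response entries), Section 3 and Section 7.3, replace the definition with that of Section 11.3.1: time from first CR/PR on combination treatment to loss of response, progression or death. State the combination-treatment start in 11.3.1 as well.
- Count new systemic cGvHD therapy as an event, since Section 9 already calls it treatment failure.
- For patients already in CR or PR at C2D1, start the clock at C2D1. Waiting for a later confirming visit would drop early losses, because the next NIH score is at week 16, and would raise the durability estimate.
- Delete the symptom wording and the clause on absence of progression since treatment initiation.
- Report durability as the Kaplan-Meier estimate, so that a first response at week 52 contributes no observed duration.
- State one reference for progression, reconciling 7.2 with 7.3, and say whether the Section 5.6 rule applies to this endpoint.

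The cost is wording only, with no new data or visits. The reported durability may be lower than under the Section 3 reading.
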